COVER PAGE

Artificial Tears, Tear Lipids and Tear Film Dynamics

NCT05705518

Document Date: 02/02/2023

STUDY PROTOCOL

Effects Of Artificial Tears on Tear Lipid Films and Tear Film Dynamics *In Vivo*

Principal Investigator:
[name], OD, PhD, FAAO¹

Co-Investigators:
[name], OD, PhD, MPH, FAAO¹
[name], OD, PhD, MBA, FAAO²

University of California, Berkeley¹
School of Optometry
[name]
[name]

Alcon Vision, LLC²
Fort Worth, TX

I. INTRODUCTION & RATIONALE

Dry eye disease (DED) is pervasive with some reports estimating over 16 million adults diagnosed with DED in the United States.¹ Currently, artificial tears remain an integral part of managing dry eyes and are mainly used for symptomatic relief. Recent studies have shown there may be therapeutic benefits with regular use of lipid based artificial tears to improve the structure of the tear film.^{2,3,4} Lipid based artificial tears have been shown to increase lipid layer thickness and improve tear film breakup time in addition to providing subjective improvements of dry eye symptoms.^{2,3,4} The ability to increase lipid layer thickness and improve tear film stability could possibly reduce evaporative dry eye disease. In this study we propose to recruit a large group of subjects spanning a range of ages and ethnicities and administer three lipid based artificial tears against a non-lipid based artificial tear to compare their effects on the subject's tear lipid film and tear film dynamics.

II. SPECIFIC AIMS

We plan to accomplish our goals by pursuing the following specific aims and testing the associated hypotheses:

Aim 1 (Primary): Determine if the change in lipid layer thickness at 3 months compared to post-run-in baseline is different between Systane Complete PF and Refresh Relieva PF

Hypothesis: The change in tear lipid layer thickness will be significantly greater with Systane Complete PF compared to Refresh Relieva PF.

Aim 2 (Exploratory): Compare the 3-month changes in tear lipid layer uniformity and tear film thinning dynamics between the Systane Complete PF and Refresh Relieva PF

Hypothesis: The 3-month change in lipid layer uniformity will be significantly better with Systane Complete PF compared to Refresh Relieva.

Hypothesis: The 3-month change in tear film dynamics will be significantly better with Systane Complete PF compared to Refresh Relieva.

Aim 3 (Exploratory): Compare the 3-month changes in tear lipid layer thickness between the Systane Complete PF and the other two lipid products (Refresh Optive Mega-3 PF, CVS Health Lubricant Eye Drop (PG 0.6%))

Hypothesis: The 3-month change in tear lipid layer thickness will be significantly greater with Systane Complete PF compared to the other lipid-containing products.

Aim 4 (Exploratory): Compare the 3-month changes in tear lipid layer uniformity and tear film thinning dynamics between the Systane Complete PF and the other two lipid products (Refresh Optive Mega-3 PF, CVS Health Lubricant Eye Drop (PG 0.6%))

Hypothesis: The 3-month change in lipid layer uniformity will be significantly greater with Systane Complete PF compared to the other lipid-containing products.

Hypothesis: The 3-month change in lipid layer uniformity and tear film dynamics will be significantly greater with Systane Complete PF compared to the other lipid-containing products.

Aim 5 (Exploratory): Compare the 3-month changes in symptoms between the Systane Complete PF and the other two products (Refresh Relieva PF, Refresh Optive Mega-3 PF, CVS Health Lubricant Eye Drop (PG 0.6%))

Hypothesis: The 3-month change in symptoms will be significantly greater with Systane Complete PF compared to the other products.

III. STUDY DESIGN

Subjects

A total of 84 subjects will complete the study with 21 subjects in each study arm. This four-visit study will be conducted at the University of California Berkeley, School of Optometry, Clinical Research Center (Berkeley, CA, USA). Subjects will be recruited via email and fliers. Subjects will be screened prior to the study visit with an IRB approved phone screening survey.

Inclusion Criteria

- Adult (≥ 18 years) subjects who have a best corrected visual acuity of 20/30 or better
- Have symptoms of dry eye (OSDI ≥ 13)

Exclusion Criteria

- Currently using any topical eye medication (not including OTC drops)
- Have known systemic health conditions that might alter tear film physiology, have a history of viral eye disease, have a history of diabetes, have a history of ocular surgery, have a history of severe ocular trauma, have an active ocular infection or inflammation, are currently using isotretinoin-derivatives, or if pregnant or breast feeding
- Contact lens wearers
- Subjects with a condition or in a situation, which in the examiner's opinion, may put the subject at significant risk, may confound the study results, or may significantly interfere with their participation in the study will be excluded.

Trial Design

This will be a prospective, double-masked, randomized, controlled, parallel-group study designed to compare the impact of Systane Complete PF artificial tears on tear lipid layer thickness compared with a control, Refresh Relieva PF. Secondarily, the study will compare the differences in changes in tear lipid layer thickness, lipid layer uniformity, tear film thinning dynamics, and symptoms between Systane Complete PF and other study products (Refresh Optive Mega-3 PF and CVS Health Lubricant Eye Drop (PG 0.6%)). The study will include 4 clinic visits, including one week of single-masked run-in with Systane Ultra PF followed by 3 months of study treatment dosing. Participants will be asked to instill drops QID, regardless of assigned drops, throughout the study period.

Visit Schedule will be as follows:

Outcomes

Primary: Mean change from post-run-in baseline at 3 months in tear lipid layer thickness (Systane Complete PF vs Refresh Relieva PF)

Secondary:

- Mean change from post-run-in baseline at 3 months in tear lipid layer uniformity (Systane Complete PF vs Refresh Relieva PF)
- Mean change from post-run-in baseline at 3 months in tear film thinning rate (Systane Complete PF vs Refresh Relieva PF)

Exploratory:

- Mean change from post-run-in baseline at 1 and 3 months in tear lipid layer thickness (Systane Complete PF vs all lipid drops)
- Mean change from post-run-in baseline at 1 and 3 months in tear lipid layer uniformity (Systane Complete PF vs all lipid drops)
- Mean change from post-run-in baseline at 1 and 3 months in tear film thinning rate (Systane Complete PF vs all lipid drops)
- Mean change from post-run-in baseline at 1 and 3 months in symptoms (Systane Complete PF vs all lipid drops)

Sample Size

The primary outcome of this study will be the difference in mean 3-month change in tear lipid layer thickness between Systane Complete PF and Refresh Relieva PF. Fogt and colleagues were able to establish statistical significance in the differences in short-term (15 min) change from baseline in tear lipid layer thickness when comparing a lipid-emulsion to non-emulsion in two separate studies with 20 subjects (10 subjects/arm).^{3, 4} In this study we are implementing a complete 3-month treatment regimen, and additionally will increase the target sample size to N=84 (4 study arms, 21 subjects/arm), and therefore can be reasonably assured of having sufficient statistical power to detect any treatment-control differences that may present.

Surveys and Clinical Tests

Clinical measurements will be obtained from both eyes of each subject and testing will be performed in the below order. Testing order was designed to sequentially administer the least invasive to most invasive test. This methodology will ensure that a previous procedure will have a minimal effect on subsequent assessments

Study Visit

A. Baseline/Screening Visit

(Visit 1A)

1. Subject History, Eligibility, Informed Consent: Subjects will be asked to repeat the IRB approved screening survey at the study visit to verify that they are still eligible for the study. Non-eligible subjects will be dismissed or rescheduled depending upon the reason for ineligibility. Eligible subjects will be enrolled, consented, and requested to sign a privacy document.

2. Baseline Questionnaires: Subjects demographics, lifestyle, ocular and medical history will be collected. They will be asked to complete the PSQ, Likert, DEFC, SPEED II, OSDI, VAS, SANDE, and DEQ-5 questionnaires to determine baseline comfort.

(Visit 1B)

1. Baseline Visual Acuity: The subject's habitual visual acuity will be measured.

2. Tear Lipid Layer Thickness and Blinks: The Lipiview interferometer will be used to determine the subject's tear lipid layer thickness and blinks.

3. Tear Meniscus Height, Ocular Redness, and Keratometry: The Oculus Keratograph 5M will be used to determine the tear meniscus height, redness, and curvature of the eyes.

4. Non-Invasive Tear Breakup Time (NITBUT): The Oculus Keratograph 5M and Medmont Topographer will be used to determine NITBUT with the machine's standard software by taking one to three successive measurements.

5. Slit-Lamp Biomicroscopy: The investigator will use a slit-lamp biomicroscope to document normal and/or remarkable findings of the anterior eye structures: eyelashes (blepharitis), eyelids, conjunctiva, and cornea.

6. Fluorescein Tear Breakup Time (FTBUT): The investigator will instill 1 μ l of 1% w/v of sodium fluorescein by pipette and take 3 successive measurements for each eye.

7. Slit Lamp Recordings with EasyTear View: Capture videos with diffuse white light and cobalt blue light to analyze tear film lipids (thickness and uniformity) and tear film thinning dynamics.

8. Schirmer's Test: Investigator will use a modified technique³ for aqueous tear production rate measurement.

9. Meibomian Gland Expression: The investigator will use the Korb Meibomian gland expressor to apply pressure along both the upper and lower eyelids and score gland secretion quality on central/nasal/temporal regions of each lid (i.e., ~5 glands in each region) with scores ranging from 0-3 (0=no secretion, 1=inspissated, 2=cloudy, 3=clear), such that each lid will have a maximum score of 45.

10. Lissamine Green Evaluation: The investigator will evaluate the quality of the front surface of the eyes by instilling a small amount of lissamine green ophthalmic dye.

11. Meibography: The Oculus Keratograph 5M will be used to image the tear glands (e.g., Meibomian glands) of the upper and lower eyelids.

12. Dispense Run-In Drops and Instructions: Investigators will dispense one week's worth of Systane Ultra PF (label removed) to all qualified, enrolled subjects and instruct them to instill drops 4 times daily for one week. Patients are then scheduled for their next visit at least 90 minutes after their planned last dose.

B. Visit 2: Post-Run-In Period, Randomization, Treatment

1. Subject History: Subjects will be asked to confirm any changes to medical or ocular history.

2. Questionnaires: Subjects will be asked to complete an abbreviated questionnaire package to determine comfort.

3. Visual Acuity: The subject's habitual visual acuity will be measured.

4. Tear Lipid Layer Thickness and Blinks: The Lipiview interferometer will be used to re-assess the subject's tear lipid layer thickness and blinks.

5. Tear Meniscus Height, Ocular Redness, and Keratometry: The Oculus Keratograph 5M will be used to determine the tear meniscus height, redness, and curvature of the eyes.

6. Non-Invasive Tear Breakup Time (NITBUT): The Oculus Keratograph 5M will be used to determine NITBUT with the machine's standard software by taking three successive measurements.

7. Slit-Lamp Biomicroscopy: The investigator will use a slit-lamp biomicroscope to document normal and/or remarkable findings of the anterior eye structures: eyelashes (blepharitis), eyelids, conjunctiva, and cornea.

8. Fluorescein Tear Breakup Time (FTBUT): The investigator will instill 1 μ l of 1% w/v of sodium fluorescein by pipette and take 3 successive measurements for each eye.

9. Slit Lamp Recordings with EasyTear View: Capture videos with diffuse white light and cobalt blue light to analyze tear film lipids (thickness and uniformity) and tear film thinning dynamics.

10. Confocal Microscope: The confocal microscope will be used to examine anatomy and physiology of the front surface of the eyes.

11. Randomize, Dispense Study Drops, and Instructions: Subjects will be randomized to one of four study drops (Refresh Relieva PF, Systane Complete PF, Refresh Optive Mega-3 PF, or CVS Health Lubricant Eye Drop (PG 0.6%)). Investigators will dispense a 1-month supply of the assigned study drops and provide instructions to instill drops 4 times daily for 3 months. Patients are then scheduled for their 1-month follow-up visit, ensuring visit is scheduled at least 90 minutes after their planned last dose.

C. Visit 3: One Month Follow-Up

1. Repeat measurements (Part B) 1-9 and 11 from baseline visit.

2. Dispense study drops. The investigator will dispense drops for the next two months and schedule the follow-up phone call at 2 months and the final visit at 3 months.

D. Phone Call: Two Month Follow-Up

1. Subject History: Subjects will be asked to confirm any changes to medical or ocular history.

2. Follow-up to ensure no changes in habitual regimen, protocol is being followed, supply of drops is adequate to reach the end of the study.

3. Questionnaires: Subjects will be asked to complete an abbreviated questionnaire package to determine comfort.

E. Visit 4: Three Month Follow-Up

1. Repeat measurements (Part B) 1-10 from baseline visit.

2. Exit Visual Acuity: The subject's habitual visual acuity will be measured.

3. Study Completion: Subjects will be compensated for their time and exited from the study.

F. Schedule of Study Procedures and Assessments

Procedure/Assessment	Visit 1	Visit 2	Visit 3	Phone Call	Visit 4
Inclusion/Exclusion	✓				
Informed Consent	✓				
Demographics	✓				
Medical and Ocular History	✓	✓	✓	✓	✓
PSQ, Likert, DEFC, SPEED II, OSDI, VAS, SANDE, & DEQ-5	✓	✓	✓	✓	✓
Randomization		✓			
Visual Acuity	✓	✓	✓		✓
Tear Lipid Layer Thickness and Blinks	✓	✓	✓		✓

Tear Meniscus Height, Ocular Redness and Keratometry	✓	✓	✓		✓
Non-Invasive Tear Breakup Time	✓	✓	✓		✓
Slit-Lamp Exam	✓	✓	✓		✓
Fluorescein Tear Breakup Time	✓	✓	✓		✓
Easy TearView Recordings	✓	✓	✓		✓
Schirmer's Test	✓		✓		✓
Meibomian Gland Expression	✓				✓
Lissamine Green Evaluation	✓				
Meibography	✓				
Confocal Microscope		✓			✓
Adverse Events		✓	✓	✓	✓
Exit					✓

Data Analysis

Primary Model (Aim 1):

- The primary outcome of tear lipid layer thickness (LipiView) change from post-run-in baseline to 3 months will be analyzed using a repeated measures mixed effects model. This modeling approach will produce an unbiased estimate of the treatment effects (Systane Complete PF vs. Refresh Relieva PF), while accounting for the internal correlations engendered by the repeated measures study design (repeat visits, two eyes per subject).

Additional Analyses (Aims 2-5, Exploratory):

- The same modeling approach will be employed to analyze the changes from post-run-in baseline to 3 months in tear lipid layer uniformity and in tear thinning time between the Treatment (Systane Complete PF) and Control (Refresh Relieva PF) solutions.
- The same modeling approach will be employed to analyze changes from post-run-in baseline to 3 months in lipid layer thickness and uniformity, tear thinning time, and symptom scores among 3 solutions (Systane Complete PF, Refresh Optive Mega-3 PF, CVS Health Lubricant Eye Drop (PG 0.6%)).
- Additional exploratory modeling for all outcomes will be performed to determine the impact of baseline subject characteristics including demographics, visual acuity, tear film stability (NITBUT and FTBUT), tear production (Schirmer's), and any ocular surface findings.
- Exploratory models will be assessed by F-test p-values, residual and other diagnostic plots, fit statistics such as the log-likelihood and the AIC, and clinical relevance of effect sizes. Both additive and interaction models will be examined.
- All study variables will also be subjected to a thorough descriptive analysis, in order to better understand the modeling results and the relationships among the model variables. This analysis will include descriptive statistics (minimum, maximum, median, mean, SD), histograms of the distributions of continuous variables (including lipid layer thickness and coefficient of variation, tear thinning rate, non-invasive and fluorescein tear breakup times, modified Schirmer strip wetted lengths and tear production rate, and symptom questionnaire scores), and tabulations of ordinal and categorical variables (including clinical grades of the anterior eye structures cornea, conjunctiva, eyelids and lashes).
- Additional exploratory analyses will examine the basic univariate relationships between the model outcome variables and potential explanatory variables via box-and-whisker plots, scatterplots, and simple linear regressions / t-tests / univariate ANOVA models (as appropriate for the data types).

IV. Study Timeline

	2022	2022	2022	2023	2023	2023	2023	2023	2023	2023	2023
	Oct	Nov	Dec	Jan	Feb	Mar	April	May	June	July	Aug
Activity											
Contracting											
IRB Preparation											
Data Collection											
Data Analysis											
Final Study Report											

VI. Publication Plans

An abstract describing the comparison of tear film lipid layer between Systane Complete and Refresh Relieva will be submitted for presentation at American Academy of Optometry 2023. A manuscript describing the initial drop experience and drop comfort data will be submitted to *Optometry and Vision Science or Contact Lens and Anterior Eye or Eye and Contact Lens, or Scientific Reports*.

References

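### The Sample Size section claims power for any treatment-control difference, but 21 per arm detects about 0.89 SD at 80% power (assumed two-sided 5% t-test)

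*Combined protocol and SAP*

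**What the plan says.** The Subjects paragraph fixes the size: "A total of 84 subjects will complete the study with 21 subjects in each study arm". The Trial Design paragraph describes a "prospective, double-masked, randomized, controlled, parallel-group study", and the primary outcome is the 3-month change in lipid layer thickness, Systane Complete PF against Refresh Relieva PF.

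The Sample Size section justifies the number by precedent. Two earlier studies, each described as 20 subjects at 10 per arm, found significant differences in "short-term (15 min) change from baseline in tear lipid layer thickness". Because this trial treats for 3 months and enrols 21 per arm, the section concludes that it "can be reasonably assured of having sufficient statistical power to detect any treatment-control differences that may present".

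No alpha, numerical power, SD of the 3-month change or target difference is stated anywhere. Sidedness is also open. Aim 1 asks whether the change "compared to post-run-in baseline is different between Systane Complete PF and Refresh Relieva PF", while its hypothesis reads "The change in tear lipid layer thickness will be significantly greater with Systane Complete PF compared to Refresh Relieva PF". The Data Analysis section plans a mixed model for a "repeated measures study design (repeat visits, two eyes per subject") and gives no correlations.

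**The concern.** The conclusion is too broad for any fixed sample size: for a small enough true difference, power is close to alpha whatever the SD or model.

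The precedent does not narrow the gap. Significance in an earlier study is not an estimate of power in a new one, and no effect size or SD is carried over. The time scale differs (15 minutes against 3 months). So does the design, at least in part, since the title of reference 3 ends "Omega-3 Fatty Acids: A Randomized, Double-Masked, Crossover Study" and a within-subject comparison does not have the precision of a between-subject one. The section also cites the total of 84, although the primary comparison uses only two arms: 2 × 21 = 42 subjects.

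What is at stake is how the primary result will be read. A reader told that the trial can detect any difference may take a non-significant result as evidence of no difference.

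**Working it through.** **The plan's own figure.** N = 84 cannot be reproduced. There is no alpha, power, difference or SD to put into a formula, so the check runs the other way: what can 21 against 21 detect?

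**Inputs**
- n = 21 completers per arm (Subjects; Sample Size).
- Two-sided alpha of 0.05: assumed. A one-sided 5% test is shown as an alternative.
- Two-sample t-test on each subject's 3-month change, averaged over both eyes: assumed. Differences are in units of the between-subject SD of that change, because no SD in nm is given.
- The 0.5 SD benchmark is an illustration and has no source in the documents.

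**Power.** For a true difference of δ SD, the noncentrality is λ = δ√(n/2) = 3.240δ, with df = 2 × 21 − 2 = 40 and critical value c = t(0.975, 40) = 2.021. Power = 1 − F(c; 40, λ) + F(−c; 40, λ), where F is the noncentral t distribution function.

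| True difference (SD) | Power |
|---|---|
| 0.2 | 9.7% |
| 0.3 | 15.8% |
| 0.5 (λ = 1.620) | 35.3% |
| 0.8 | 71.6% |
| 1.0 | 88.5% |

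Solving for δ gives 0.886 SD at 80% power and 1.025 SD at 90%. The normal approximation is close: (1.960 + 0.842) × √(2/21) = 0.865 SD at 80%.

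**Range over the unstated choices**

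| Test | 80% power | 90% power | Power at 0.5 SD |
|---|---|---|---|
| Two-sided 5%, df 40 | 0.886 SD | 1.025 SD | 35.3% |
| Two-sided 5%, error pooled over four arms (df 80, equal variances assumed) | 0.875 SD | 1.013 SD | 36.0% |
| One-sided 5%, df 40 | 0.781 SD | 0.919 SD | 47.9% |

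**Two eyes.** The gain from averaging the eyes is already inside the subject-level SD. In per-eye SD units the factor is √((1 + ρ)/2). At an assumed inter-eye correlation ρ of 0.3, this gives 0.886 × 0.806 = 0.71 SD detectable at 80% power, and 50% power at 0.5 per-eye SD. At ρ = 1 the figures return to 0.89 SD and 35%.

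**Loss to follow-up.** The figures take 21 per arm as completers. With 18 per arm (assumed), the detectable difference at 80% power is 0.96 SD.

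**What a non-significant result would leave open.** The 95% CI half-width is t(0.975, 40) × √(2/21) = 2.021 × 0.3086 = 0.624 SD. An observed difference of exactly zero gives −0.62 to +0.62 SD. An observed 0.5 SD, which would not be significant, gives −0.12 to +1.12 SD.

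**The case against.** The best defence is that the plan contains no calculation, so no calculation is wrong, and that the sentence is loose prose, softened by its own hedge. Nothing shows the trial is too small: no SD or relevant difference in nm is given, 0.5 SD is only a benchmark, and quoting 35% alone would overstate the case while sidedness is open. Those last points stand, so the one-sided 47.9% belongs beside the 35%, and no claim is made that the trial is underpowered for its real target. The hedge softens the certainty of the sentence but not its scope.

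A second argument is that the planned mixed model may do better than a t-test. If the treatment effect were pooled over months 1 and 3 (assumed correlation of changes 0.3 to 0.9, equal variances and effects), the detectable difference at 80% power would be about 0.71 to 0.86 SD. Baseline adjustment (assumed correlation of baseline with change 0.3 to 0.6) would give about 0.85 to 0.71 SD. However, the Data Analysis section states no such terms, and pooling visits would estimate something other than the 3-month change. A contrast at 3 months with separate effects per visit gains nothing with complete data. None of these variants supports a claim about *any* difference.

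Third, the harm is one of interpretation: the aim is superiority, no equivalence claim is planned, and conduct and the primary estimate are unaffected. That is true, and it limits the weight of the point. But this sentence is the plan's only statement about power, and the Publication Plans section foresees an abstract on exactly this comparison.

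**Conclusion.** The concern holds. The power statement is wrong as written under any alpha, SD or model, and the 15-minute precedents do not support it. Under the assumed two-sided 5% t-test on the subject-level change with 21 completers per arm, the trial detects 0.89 SD at 80% power and 1.03 SD at 90%. The most favourable reading of the unstated alpha and sidedness considered here (one-sided 5%) gives 0.78 and 0.92 SD. Power at 0.5 SD lies between 35% and 48% over these test choices. Whether that is adequate cannot be judged, because the documents name neither an SD nor a difference that matters. The design can stand; the sentence should be corrected.

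**What to change.** Keep N. Delete the claim about any difference and stop using the 15-minute studies as evidence of power for the 3-month endpoint. They may remain as background. Possible replacement:

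> The primary comparison uses two arms (21 completers each, 42 in total). Assuming a two-sided alpha of 0.05 and a two-sample t-test on the subject-level (two-eye mean) 3-month change, as a planning approximation to the mixed-model contrast at 3 months, the study has 80% (90%) power to detect a difference of 0.89 (1.03) SD of that change. Smaller differences may be missed.

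No further reduction should be claimed for measuring two eyes, since that gain is already in the subject-level SD. The sponsor should confirm alpha and sidedness, update the figures if they differ from those assumed, and commit to reporting the primary difference with its 95% CI.

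The cost is protocol wording only: N, endpoint and planned model do not change. The stated power will look less favourable, and the sponsor must commit to an alpha and sidedness that are now open.

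### Is the 3-month endpoint visit booked without the 90-minute gap after the last drop that applies to the baseline and 1-month visits?

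*Combined protocol and SAP*

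**What the plan says.** All places are in section III of the combined protocol and SAP.

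- **Booking Visit 2** (A. Baseline/Screening, Visit 1B, item 12): "Patients are then scheduled for their next visit at least 90 minutes after their planned last dose".
- **Booking Visit 3** (B. Visit 2, item 11, titled "Randomize, Dispense Study Drops, and Instructions"): "Patients are then scheduled for their 1-month follow-up visit, ensuring visit is scheduled at least 90 minutes after their planned last dose".
- **Booking Visit 4** (C. Visit 3, item 2): staff dispense two months of drops and "schedule the follow-up phone call at 2 months and the final visit at 3 months". No interval is given.
- **Cross-references**: C. Visit 3, item 1 reads "Repeat measurements (Part B) 1-9 and 11 from baseline visit". E. Visit 4, item 1 reads "Repeat measurements (Part B) 1-10 from baseline visit".

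The Outcomes and Data Analysis sections define the primary endpoint as the change from the post-run-in baseline (Visit 2) to 3 months (Visit 4). Drops are used four times daily throughout. Trial Design also introduces a visit-schedule display that was not legible in the text available, so its content cannot be counted as absent.

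**The concern.** A change score is clean only if both ends are measured under the same conditions. At Visit 2 every subject has used the same run-in product, so any lingering effect of a recent drop is common to the arms. At Visit 4 the drop depends on the arm, so a recent drop carries a product-specific effect.

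The plan itself gives reason to care. The Introduction says lipid drops thicken the lipid layer, and the Sample Size section cites lipid versus non-lipid differences 15 minutes after a drop. If Visit 4 could be booked at any time after a dose, an acute difference could be added to a contrast meant to show three months of treatment, possibly in favour of Systane Complete PF. The mixed model cannot separate the two without dose times, and the time of the last drop is not among the listed assessments.

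**Working it through.** **Step 1. Which section is Part B?** The cross-reference matters only if item 11 is the one holding the 90-minute condition. The candidates are section B (Visit 2) and the sub-visit 1B, where item 11 is "Meibography: The Oculus Keratograph 5M will be used to image the tear glands". Each can be tested against the schedule of procedures. Adverse events and exit appear in neither list and are left out.

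| Reference | Part B = Visit 2 | Part B = Visit 1B |
|---|---|---|
| Visit 3, items 1-9 and 11 | Schirmer's is ticked but not listed: 1 mismatch | Gland expression and meibography are listed but not ticked; history and questionnaires are ticked but not listed: 4 mismatches |
| Visit 4, items 1-10 | Schirmer's and gland expression are ticked but not listed: 2 mismatches | Lissamine green is listed but not ticked; history, questionnaires and confocal are ticked but not listed: 4 mismatches |
| Total | 1 + 2 = 3 | 4 + 4 = 8 |

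The numbering also fits Visit 2 closely. Item 10 there is confocal microscopy, which Visit 3 skips and Visit 4 includes, as the schedule ticks it. Part B is Visit 2.

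**Step 2. What can be repeated from item 11?** It contains randomization, dispensing, instructions and booking. The schedule ticks randomization at Visit 2 only. What remains is dispensing, instructing and booking the next visit with the 90-minute gap. Item 11 names the 1-month visit because that was the next visit when it was written for Visit 2.

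**Step 3. Does Visit 4 leaving out item 11 matter?** No. The gap is set at the visit that does the booking, and nothing is booked after Visit 4.

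**Step 4. How much exposure if the gap were not applied at all?** The plan gives no figure to reproduce.

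- From the plan: four drops a day, 15 minutes as the only acute time, 21 subjects per arm, so 2 × 21 = 42 in the primary contrast.
- Assumed: W = 14 to 18 waking hours; k = 3 or 4 post-dose windows in waking time, not overlapping; appointments spread over waking hours and unrelated to dosing; the acute window ends at 15 minutes.

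Share of appointment times within 15 minutes of a drop: f = k × 0.25 / W.

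- Lowest: 3 × 0.25 / 18 = 4.2%; 42 × 4.2% = 1.8 subjects.
- Highest: 4 × 0.25 / 14 = 7.1%; 42 × 7.1% = 3.0 subjects.

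LipiView is fourth in the Visit 2 order ("The Lipiview interferometer will be used to re-assess the subject's tear lipid layer thickness and blinks"), after history, questionnaires and acuity. With e minutes from arrival to LipiView, f = k × max(0, 15 − e) / 60 / W, which is 0% once e reaches 15. The plan gives no durations.

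If f is equal in both arms, the contrast shifts by f × D, where D is the acute difference between products. D is not given, so the shift has no computable size.

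**The case for a change.** The strongest reply is that a condition on the primary endpoint visit should not hang on a cross-reference. Item 1 of Visit 3 speaks of measurements, and item 11 is not one. Item 2 then restates dispensing and booking and leaves the gap out. The cross-reference is also imperfect, since Schirmer's is ticked at Visits 3 and 4 but is not in Part B. The effect of a drop may outlast 15 minutes: on the same assumptions, the share of appointment times within 90 minutes of a drop runs from 3 × 1.5 / 18 = 25% to 4 × 1.5 / 14 = 43%, or about 11 to 18 of 42. Drop times not recorded at the visit would be hard to recover later.

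Some of this stands. Item 2 is less explicit than the two earlier booking steps, and masking and randomization would not remove an acute effect that differs by product.

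The rest does not carry it further. Item 11 is named on purpose in the cross-reference, and apart from randomization it has no content other than dispensing, instructing and booking. The 25% to 43% range counts appointment times that would fail the rule if staff dropped it after two bookings made under it. It measures neither an effect nor a bias, and the documents do not say how long an effect lasts between 15 and 90 minutes. The stated gaps refer to the planned dose at Visits 2 and 3 as well, so the lack of recorded times is not peculiar to Visit 4, and nothing in the plan forbids collecting them. An analysis by time since last drop would condition on behaviour after randomization and, for the 15-minute window, would rest on about 0 to 3 subjects.

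**Conclusion.** The concern does not call for a change. The observation is accurate: the step that books Visit 4 does not itself repeat the 90-minute condition. The natural reading of the Visit 3 cross-reference supplies it, and staff who have already booked two visits under the rule would be expected to book the third in the same way. On that reading both ends of the change score are measured under the same condition.

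If the gap were ignored altogether, exposure at the only acute time the plan documents would be 0% to 7% of visits, under the stated assumptions about waking hours, dosing and appointment times. The resulting bias cannot be sized from the documents. The conclusion rests on Part B meaning Visit 2, which the schedule supports (3 mismatches against 8), and on the bookable part of item 11 being repeated. The illegible visit-schedule display may also state the condition. Making the Visit 3 and Visit 2 booking steps read alike would be a one-line tidy-up, and recording the actual time of the last drop is optional. Neither corrects a wrong result.
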